- N. Hong et al., "Deep-Learning-Based Detection of Vertebral Fracture and Osteoporosis Using Lateral Spine X-Ray Radiography," J. Bone Miner. Res., vol. 38, no. 6, pp. 887–895, Apr. 2023, doi: 10.1002/jbmr.4814.
- 15. N. Yamamoto et al., "Deep Learning for Osteoporosis Classification Using Hip Radiographs and Patient Clinical Covariates," Biomolecules, vol. 10, no. 11, p. 1534, Nov. 2020, doi: 10.3390/biom10111534.
- N. M. Buderer, "Statistical methodology: I. Incorporating the prevalence of disease into the sample size calculation for sensitivity and specificity," Acad. Emerg. Med., vol. 3, no. 9, pp. 895–900, Sep. 1996, doi: 10.1111/j.1553-2712.1996.tb03538.x.
- R. Jang, J. H. Choi, N. Kim, J. S. Chang, P. W. Yoon, and C.-H. Kim, "Prediction of osteoporosis from simple hip radiography using deep learning algorithm," Sci. Rep., vol. 11, no. 1, pp. 1–9, Oct. 2021, doi: 10.1038/s41598-021-99549-6.

Questionnaire Form

	(General In	formation		
Have you had your X-ray done at Ibn Sina, Uttara within the last 3 months?		□ (1) Yes	□ (2) No		
		If yes, what type of X-ray did you do?			
		X-ray ID	D	late	
	Ρ	articipant l	Information		
Patient ID			Date of birth		
Patient's name			Occupation		
Contact no.			Gender	□ (1) Male □ (2) Female	
Is written informed consen	; obt	tained?	\Box (1) Yes	□ (2) No	
Date of interview					
Name of interviewer					
А	nth	ropometri	c information		
Height (Feet/Inches)					
Weight (Kg/Kilogram)					
		□ (1) Yes □ (2) No			
Have you had any fractures	? 1	If yes, specify the affected area			
	(Clinical In	formation		
Menopause age					
No. of Pregnancies					
Diabetes		□ (1) Yes	□ (2) No		
Cardiovascular disease		□ (1) Yes	□ (2) No		
Parent fractured hip		□ (1) Yes	□ (2) No		
Currently smoking		□ (1) Yes	□ (2) No		
Glucocorticoids		□ (1) Yes	□ (2) No		
Rheumatoid arthritis		□ (1) Yes	□ (2) No		
Secondary osteoporosis		□ (1) Yes	□ (2) No		
Alcohol 3 or more units/day		□ (1) Yes	□ (2) No		

Project Title: Development and Evaluation of an Artificial Intelligence Model for Bone Mineral Density Prediction from X-Ray Images

JUSTIFICATIONS FOR INFORMED CONSENT WAIVER (RETROSPECTIVE STUDY)

The proposed research is a study that only uses medical records of X-ray examinations and DEXA scans. As the number of samples required is large (600 according to our sample size calculation) compared to the monthly recorded cases, it is not possible to return to the patients for acquiring their consent in case of previously recorded data. Considering the high potential impact of the study, we earnestly request waiver of informed consent. The justification for this request is provided below:

1. On the topic of informed consent waiver, the regulatory authority of the United States, Department of Health and Human Services (HHS) mentions in 45 C.F.R. § 46.116(d):

"An IRB may approve a consent procedure which does not include, or which alters, some or all of the elements of informed consent set forth in this section, or waive the requirements to obtain informed consent provided the IRB finds and documents that:

(1) The research involves no more than minimal risk to the subjects;

(2) The waiver or alteration will not adversely affect the rights and welfare of the subjects;

(3) The research could not practicably be carried out without the waiver or alteration; ..."

2. On the topic of case control studies, the Bangladesh Medical Research Council (BMRC) "Ethical Guidelines for Conducting Research Studies Involving Human Subjects" mentions on Page 45:

"However, if it entails only a review of medical records, informed consent may not be required and indeed may very often not be feasible".

In light of the abovementioned regulatory guidelines described by HHS (USA) and BMRC, we want to highlight that our study fulfills all of the above conditions as explained below:

1. The proposed research involves no more than minimal risk to subjects. According to HHS document 45 C.F.R. § 46.102(i):

"Minimal risk means that the probability and magnitude of harm or discomfort anticipated in the research are not greater in and of themselves than those ordinarily encountered in daily life or during the performance of routine physical or psychological examinations or tests."

We will use de-identified medical records for the study. This falls into the category of minimal risk as described above.

- 2. The research could not be carried out practicably without the waiver or alteration. Training artificial intelligence algorithms requires a huge amount of data from a large number of patients due to the overfitting problem (further detailed in the sample size calculation section below). It is practically not possible to collect signed or verbal informed consent from each patient from each hospital.
- 3. The waiver or alteration will not adversely affect the rights and welfare of the subjects. Only their digital medical images and clinical history data will be used for the research. Personal identifying information (name, etc.) will be removed after linking data.

With the explanations provided above, we hope that the ethical review committee will be kind enough to approve our request to waive the informed consent requirement for this study using medical records. As we have mentioned above, the study is of potentially high impact and unfortunately not feasible without the waiver.

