Our goal is to create an AI-assisted diagnostic tool that can be easily integrated into clinical workflows, offering a cost-effective and accessible solution for osteoporosis screening.

• **Objectives:** The primary objective is to curate a comprehensive dataset of X-ray images sourced from publicly available domains and local health facilities, encompassing a diverse representation of patient demographics, geographic locations, and equipment variations. Building upon this dataset, we seek to develop a robust artificial intelligence model capable of prediction of bone mineral density from X-ray images.

The specific objectives of the study are:

- a) To develop a deep learning convolutional neural network (CNN) model that can accurately predict Bone Mineral Density (BMD) values from Xray images, using both prospective and retrospective data collection methods.
- b) To validate the AI model's performance on a diverse dataset encompassing a broad demographic, including variables such as age, gender, height, weight, menopausal status, and the presence of comorbidities like cardiovascular disease and diabetes.
- c) To evaluate the model's performance using a range of metrics, including Area Under the Precision-Recall Curve (AUPRC), accuracy, Mean Absolute Error (MAE), and Pearson Correlation Coefficient (PCC), ensuring its robustness in predicting BMD.
- d) To assess the usability and interpretability of the AI model's output by healthcare professionals, determining its integration into clinical practice and its impact on the diagnostic workflow efficiency.
- e) To measure the generalizability and adaptability of the model across various healthcare settings, ensuring the AI system's reliability on X-ray images from different populations and regions.

- f) To investigate the model's potential in enhancing early detection and treatment planning for osteoporosis by providing a non-invasive, cost-effective tool for BMD estimation, potentially leading to better patient management and outcomes.
- g) To assess the AI model's role as a decision support tool in determining the necessity for additional diagnostic procedures, such as DEXA scans, thereby optimizing patient care pathways and potentially reducing healthcare costs.

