- **Rationale:** The early detection and treatment of osteoporosis are crucial in preventing fractures and ensuring the quality of life for individuals at risk. However, in developing countries like Bangladesh, the standard method for assessing bone health, DEXA, is not widely accessible due to its cost and the scarcity of specialized equipment and trained personnel. Consequently, many cases of osteoporosis remain undiagnosed until a fracture occurs, which significantly impacts patient outcomes and healthcare costs.

The current pathway for osteoporosis suspicion in Bangladesh typically begins with an X-ray prompted by symptoms of pain or fracture. If osteoporosis is suspected, a subsequent BMD test is recommended. This twostep process not only increases the financial burden on patients but also delays the diagnosis and treatment of osteoporosis, especially in rural areas where BMD testing facilities are scarce.

Addressing these challenges, our research proposes the use of deep learning algorithms to predict BMD values directly from X-ray images, which are more readily available and cost-effective than DEXA scans. By training a CNN with a dataset that includes demographic and clinical covariates, such as age, gender, menopausal status, cardiovascular disease, and diabetes, our AI model aims to identify correlations that can accurately predict BMD [15]. In this way, the developed AI model is intended to function as an assistive tool, providing a preliminary assessment to guide physicians on whether a more expensive and resource-intensive DEXA scan is warranted. This approach could substantially streamline the diagnostic process, making it more efficient and potentially reducing unnecessary medical expenses for patients.

- **Methodology:** In our data-driven approach to developing a predictive model for Bone Mineral Density (BMD) from X-ray images, we will collect and utilize a comprehensive dataset that includes X-ray images and BMD reports alongside demographic and clinical details of the subjects. The methodology will ensure patient privacy and data security, with all personally identifiable information being excluded from the dataset.

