- d) **Methods of Data Collection:** The following fields will be recorded in the data collection for this study:
 - Patient ID (unique identification number)
 - Date & time of the data input
 - Age
 - Gender
 - Phone number
 - X-ray image (hip or spine)

- DEXA scan result
- BMI
- Menopausal status
- Diabetes
- Cardiovascular disease and other clinical covariates

The X-ray images, and DEXA scan result of the subjects along with the relevant clinical covariates will be used to design the algorithms. The standard test status and the corresponding result will be used as the ground truth for our detection algorithm.

e) **Data Interpretation:** Upon the conclusion of data collection, exploratory data analysis to assess the distribution of patients across different demographics and clinical factors, including age, gender, menopausal status, presence of cardiovascular diseases, diabetes, and their correlation with BMD values. This process will ensure a comprehensive understanding of the dataset's characteristics and the establishment of a balanced dataset that represents a wide spectrum of patient profiles.

The refined dataset will serve as the foundation for training and evaluating our AI model, specifically designed for the regressionbased prediction of BMD from X-ray images. Our AI algorithm will leverage CNN to process X-ray images and predict BMD values, aiming to identify potential cases of osteopenia, osteoporosis, and normal.

To ascertain the model's performance and its clinical applicability, we will compare the AI-generated predictions with actual BMD measurements obtained from DEXA scans. This validation process will involve collaboration with orthopedic specialists and radiologists who will review the AI predictions in the context of their clinical experience and available patient information.

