f) Statistical Analysis: Upon finalizing the dataset, our statistical analysis will concentrate on evaluating the artificial intelligence model's capability to predict BMD from X-ray images accurately. Performance metrics such as Mean Absolute Error (MAE), Pearson Correlation Coefficient (PCC), Area Under the Precision-Recall Curve (AUPRC), and accuracy will be employed to meticulously assess the model's performance. To ensure the reliability of our findings, we will implement k-fold cross-validation techniques, providing a framework for evaluating our model across various subsets of data. This approach will allow us to calculate mean values and standard deviations for each performance metric, offering a comprehensive understanding of the model's predictive accuracy and consistency. The culmination of our analysis will involve a comparative review of different CNN architectures and training methodologies to determine the most effective strategy for BMD prediction from X-ray images.

Utilization of Results: The study results will play a crucial role in the development and evaluation of an automatic BMD prediction algorithm for osteoporosis screening. The algorithm's primary objectives are:

a) BMD Prediction: To accurately predict BMD values from X-ray images, facilitating an automated assessment tool for early detection of osteoporosis and osteopenia. This tool aims to bridge the gap in accessibility to BMD testing, especially in resource-limited settings.

b) Clinical Decision Support: To aid healthcare professionals by providing automated BMD assessments, enhancing their ability to make informed decisions regarding patient care. The model's predictions can help prioritize patients who need further testing or intervention, streamlining the diagnostic process.

c) Correlation Analysis: To explore and identify significant relationships between BMD or osteoporosis and collected clinical covariates such as age, gender, menopausal status, cardiovascular diseases, and diabetes. This analysis aims to enhance understanding of the factors influencing bone health, contributing to personalized and more precise osteoporosis risk assessment and management strategies.

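### The prospective questionnaire asks only for age at menopause, so a woman's blank entry leaves unclear the menopausal status that the protocol says it will record and analyse (minor)

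*Protocol*

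**What the plan says.** The Protocol calls for menopausal status in five places:

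- Objectives, b): the model is to be validated on a diverse dataset, "including variables such as age, gender, height, weight, menopausal status, and the presence of comorbidities like cardiovascular disease and diabetes".
- Rationale: the network is trained with covariates "such as age, gender, menopausal status, cardiovascular disease, and diabetes, our AI model aims to identify correlations".
- Methodology d), Methods of Data Collection: "Menopausal status" is one of the fields to be recorded.
- Methodology e), Data Interpretation: the exploratory analysis covers factors "including age, gender, menopausal status, presence of cardiovascular diseases, diabetes, and their correlation with BMD values".
- Utilization of Results, c): the correlation analysis uses "collected clinical covariates such as age, gender, menopausal status, cardiovascular diseases, and diabetes".

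The Questionnaire Form, under Clinical Information, has one menopause item, "Menopause age". It is an open entry. The items from diabetes down to alcohol each have a yes/no box, and the fracture item asks yes/no and then for detail if yes. The protocol does not say how status is derived from age at menopause or how an empty entry is coded.

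**The concern.** The field that the protocol promises is a status; the form collects an age that exists only for women who have passed menopause. Adults of either gender from 18 upward are eligible, so premenopausal women are expected, and for them an empty entry is a legitimate answer. A postmenopausal woman who cannot recall the age, or who was not asked, leaves the same empty entry.

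At stake is the quality of one covariate. If empty entries are read as premenopausal, postmenopausal women, whose BMD is expected to be lower, are mixed into the comparison group. The menopause–BMD relation in the exploratory and correlation analyses then tends to look weaker than it is, and the model may be trained on a partly wrong input.

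**Working it through.** **No plan figure to reproduce.** The protocol gives no number for this variable. Its only calculation is the sample size (335 for sensitivity, 526 for specificity, target 600). Menopausal status does not enter it.

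**What each entry reveals about a prospective participant**

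| Entry | What can be concluded |
|---|---|
| Gender box: male | Not applicable; no ambiguity |
| Female, age at menopause given | Postmenopausal |
| Female, entry empty | Premenopausal, or postmenopausal with age unknown, or not asked |

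Only the third row is a problem. Date of birth is on the form and could support a guess. But status assigned from age is a function of age, which is already a separate covariate, so the guess adds little beyond age itself.

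**Illustration of size.** Both inputs are assumptions; the documents give neither.

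- q = share of women who are postmenopausal
- m = share of postmenopausal women whose entry is empty
- All premenopausal women leave the entry empty, and every empty entry is read as premenopausal

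Share of empty entries that are really postmenopausal: f = q·m / ((1 − q) + q·m)

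| q | m | Calculation | f |
|---|---|---|---|
| 0.5 | 0.05 | 0.025 / 0.525 | 4.8% |
| 0.5 | 0.10 | 0.050 / 0.550 | 9.1% |
| 0.5 | 0.20 | 0.100 / 0.600 | 16.7% |
| 0.7 | 0.05 | 0.035 / 0.335 | 10.4% |
| 0.7 | 0.10 | 0.070 / 0.370 | 18.9% |
| 0.7 | 0.20 | 0.140 / 0.440 | 31.8% |

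At q = 0.9 the same formula gives 31.0% (0.045 / 0.145) to 64.3% (0.180 / 0.280), so the result depends heavily on an input that nobody has stated.

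**What this does to the relation.** Let D be the true difference in mean BMD between the two groups. If women with an empty entry have the same mean BMD as other postmenopausal women, the observed difference is D·(1 − f). For f from 4.8% to 31.8% this is 0.952·D to 0.682·D. If those women are older, with lower BMD than other postmenopausal women, the dilution is greater.

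**The case against.** The strongest reply is that the protocol does list status as a recorded field, and that coding rules for empty entries commonly sit in an SAP or data-management document, neither of which is shown. The form is also completed at interview, so the interviewer could write *not yet* or *unknown* in the open space. Age could classify women well away from the transition. Patient ID and phone number are recorded, and identifiers are removed only after linkage, so there is time for queries.

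Much of this stands, and it limits the point. It does not remove it: a later rule can say how to treat an empty entry but cannot supply an answer that was never requested, and neither the form nor the protocol tells the interviewer what to write.

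Several stronger readings are tempting, but the documents do not support them:

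- *Men are confounded with premenopausal women.* The gender box separates them.
- *Empty entries must be coded premenopausal or dropped.* An unknown code, imputation or an age-based guess are also open, whatever their limits.
- *The loss cannot be repaired.* Queries are possible until identifiers are removed, and age remains for partial repair.
- *Performance by menopausal subgroup will be biased.* Objective b) names the variable, but no performance estimate by menopausal status is specified; the metrics under Statistical Analysis are for the model overall.
- *The whole dataset is affected.* The retrospective data come from the clinic database, not from this form, and the prospective share of the 600 is not given.

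Finally, the form was read from a PDF. Boxes in neighbouring rows survived, so a lost box in this row is unlikely, but it cannot be excluded.

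**Conclusion.** The mismatch is real and minor. The form as shown does not carry the status field that Methodology d) promises, and the ambiguity is confined to women with an empty entry in the prospective arm. If such entries are read as premenopausal, the menopause–BMD relation tends to be diluted.

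The range of about 5–32% of empty entries misread is an illustration, not an estimate. It rests on assumed values of 50–70% postmenopausal and 5–20% non-response, and on the coding rule just described. No effect on MAE, PCC, AUPRC or accuracy has been shown. The sample size and the DEXA reference standard are untouched.

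**What to change.** Before prospective collection starts, replace the item with: *Menopause: (1) Yes (2) No (3) Not applicable (male) (4) Unknown; if yes, age at menopause.*

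Derive status from the box. If the box was missed but an age at menopause is recorded, treat the woman as postmenopausal, so that a valid answer is not discarded. In the retrospective records, code status as unknown unless it is stated; do not default to premenopausal.

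The cost is one tick-box line on the form and a one-sentence derivation rule. The small downside is an explicit unknown category, which the analyses will have to carry, mainly for retrospective records.
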